4.6.2 Statistical analysis methods

The primary analysis of efficacy will be conducted under the intention-to-treat principle; all randomized participants will be included in the analyses. All results will be analyzed with 2-sided level of significance of 0.05. Given the rapid assessment of the primary outcomes of progression, and the expected absence of loss to follow-up, we will compare the proportions of progression events between the two study arms rather than the times to progressions. The primary analysis will use the Z-test for comparison of proportions. Secondary analyses will include adjusting the intervention effect for demographics, exposure characteristics, and severity of disease upon admission, using logistic regression models.

4.6.3 Planned subgroup analyses

We will explore whether the following variables modify treatment effect: age, sex, disease severity (admission to ICU at randomization versus not) and presence or absence of comorbidities.

5. Program Management and Sub-studies

5.1 Safety Monitoring and Reporting

Chloroquine and azithromycin have been extensively studied and have been used for many years and in many hundreds or thousands of patients, and their adverse effects profiles are well described. COVID-19 has been described in more than 400,000 patients and the clinical manifestations have also been extensively described.

All information concerning adverse events will be systematically collected, all data on safety and outcomes will be reviewed regularly by the independent DSMC and sent to regulatory authorities on a monthly basis.

5.1.1 Serious adverse events

For the purposes of this trial, study efficacy and safety outcomes, known adverse effects of study medications, and events that are expected to occur with high frequency in patients with COVID-19 infection will be captured on the CRF and will be exempted from the expedited reporting. All of these events will be included in the final study report and reviewed by the DSMC on an ongoing basis.

Only those events that are both serious and unexpected for the patient population under study and who are being treated with study medication will be reported to the regulatory agency in an expedited manner.

Adverse events that are not serious, but which lead to permanent discontinuation of study medication will be recorded and included in the final study report.

5.2 Data Management

Data management will be performed by the PHRI in accordance with PHRI standards and procedures for collection and validation of data. Data will be collected on electronic case report forms (eCRFs) using an electronic data capture system, based on the availability of data in the site's electronic medical record. It is the Investigator's responsibility to ensure the accuracy, completeness, legibility, and timeliness of the data reported on the patient's eCRF. All data will be kept secure and confidentiality of all study patients will be carefully protected. Data will be validated, managed, and stored in a de-identified database on a secure server at PHRI.

5.3 Treatment Compliance Adherence

Participant treatment compliance will be documented.

5.4 Handling of Treatment Modification or Discontinuation

Prescribed study medication should be continued for the full course whenever possible. If the medication is stopped, the investigator should determine if treatment can be modified or re-initiated.

5.4.1 Study Drug Discontinuation

If the medication is discontinued, patients will be followed up according to the study procedures as specified in this protocol, up to the scheduled date of study completion, or up to recovery or stabilization of any serious and unexpected adverse event to be followed-up as specified in this protocol, whichever occurs last.

5.5 Withdrawal from the Study

Any participant who discontinues study treatment will continue follow-up assessments through to the designated final visit with the exception of those patients who withdraw consent for follow-up. If this occurs, the reason for withdrawal must be documented. Data already collected from participants requesting withdrawal will not be deleted, in order to maintain scientific integrity of the study. Withdrawn patients will not be replaced.

5.6 Sub-studies

The steering committee may add sub-studies based on participating investigators' interests. Sub-studies of interest may relate to virology, biochemical parameters, imaging, etc.

5.7 Data Safety Monitoring Committee (DSMC)

An independent DSMC will review the accumulating study data after approximately every 50 patients have been randomized (the frequency of review can be adjusted at their discretion based on emerging data) and make recommendations to the study leadership about the conduct of the trial, integrity of the data and trial discontinuation to ensure the overall safety of patients. The guiding policies and operating procedures governing the DSMC will be described in a separate DSMC charter. The DSMC will follow a flexible pragmatic monitoring approach for efficacy, considering each trial separately. They will follow a modified Haybittle-Peto boundary of 3 SD for benefit and harm as a general guideline. They will also be looking for consistency of efficacy results across both trials prior to recommending stopping any trial early. No modification of the level of significance of the final results is necessary with the higher 3 SD boundary for the Haybittle-Peto criteria.

The DSMC will also be monitoring the safety of the participants, focusing on adverse events and other safety indicators. Adverse events will be sent to the DSMC chair on a regular basis (e.g., after the first 50 patients in each trial and every month thereafter).

6. Study Organization

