Total number	1) Outpatient trial
of subjects:	Minimum total sample size required is N= 1000 (500 in each arm); it will provide 90% statistical power to detect a 50% relative risk reduction (RRR) in the proportion developing the primary outcome, assuming an usual care risk of progression of 12%.
	2) Inpatient trial
	Minimum total sample size required is N=530 (265 in each arm) in order to have 90% statistical power to detect a 40% RRR in the proportion progressing to mechanical ventilation or mortality, assuming an usual care risk of progression of 30%.

Study Intervention (both trials)

Patients will be randomly allocated to an active group that will receive chloroquine for a total of 7 days plus azithromycin for 5 days plus usual care **or** to usual care, as follows:

Chloroquine

Adults with a bodyweight \geq 50 kg: 500 mg twice daily for 7 days Adults with a bodyweight < 50 kg: 500 mg twice daily on days 1 and 2, followed by 500 mg once daily for days 3 -7

Azithromycin

500 mg on day 1 followed by 250 mg once daily for 4 days

Statistical Considerations

Randomization: In both trials, randomization will be done within center, in randomly permuted blocks.

Adaptive design features (both trials):

- Adaptive termination: A Data & Safety Monitoring Committee (DSMC) will follow a flexible pragmatic monitoring approach for efficacy and safety, considering each trial separately. They will review accumulating data after every 50 subjects have been randomized (with the ability to modify frequency of their review as dictated by the emerging data) and will only stop the trial if there is proof beyond reasonable doubt of efficacy (modified Haybittle-Peto boundary of 3 standard deviation (SD) for benefit or harm as a general guideline). They will also look for consistency of efficacy results across both trials prior to recommending early stopping for a trial.
- Adaptive intervention arms: The DSMC and the Study investigators will keep abreast of other ongoing trials and, if another promising intervention emerges, they may recommend adding (or replacing) one or more arms with the new promising intervention(s).

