4.3.3 Adaptive design features

Adaptive intervention arms: The DSMC and the Steering Committee will keep abreast of other ongoing trials and if other promising interventions emerge, may recommend adding (or replacing) one arm with the new promising intervention. They will assess the results of the translational objectives when available and may add a chloroquine loading dose if a large reduction in viral titres is not observed with the current regimen.

Adaptive sample size: Sample size calculations are based on disease progression rates that are not well known. We remain flexible, and the DSMC will be monitoring the possibility that the assumptions for sample size calculations may be modified with emerging information from this trial or other ongoing trials. If recruitment is going well, the steering committee may decide to extend recruitment as long as the independent DSMC does not terminate the trial for clear evidence of efficacy, futility (low probability) to detect a clinically meaningful difference (e.g. a 20% RRR in events) or concerns about safety.

Note, the DSMC will review the data from the two trials to make its decisions.

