4.6 Statistical Considerations

4.6.1 Sample size calculation

The minimum sample size required is **N=530** (265 in each intervention arm) in order to have 90% statistical power to detect a 40% relative risk reduction (RRR) in the proportion progressing to mechanical ventilation or death, assuming a standard-of-care risk of progression of 30%. Since patients will be hospitalized, we assumed minimal (<1%) loss to follow-up.

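### The synopsis and body disagree on the grounds for early stopping, and the cross-trial consistency check makes no exception for harm

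*Protocol*

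**What the plan says.** The protocol describes early stopping in three places.

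- **Synopsis, Statistical Considerations (adaptive termination).** The DSMC monitors efficacy and safety, taking each trial separately, and "will only stop the trial if there is proof beyond reasonable doubt of efficacy". A bracket then gives a modified Haybittle-Peto limit of 3 SD for benefit or harm, as a general guideline. The bullet ends with a check that efficacy results agree across the two trials before early stopping.
- **Sections 3.3.3 and 4.3.3.** Recruitment may be extended as long as the DSMC does not, in the inpatient wording, "terminate the trial for clear evidence of efficacy, futility (low probability) to detect a clinically meaningful difference" or for concerns about safety. Section 3.3.3 lists the same grounds.
- **Section 5.7.** "They will follow a modified Haybittle-Peto boundary of 3 SD for benefit and harm as a general guideline". The next sentence reads: "They will also be looking for consistency of efficacy results across both trials prior to recommending stopping any trial early". A separate paragraph has the DSMC watch adverse events and other safety indicators, with no SD threshold. Operating procedures are left to a charter.

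**The concern.** There are two defects of wording.

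First, the grounds for stopping do not match. Taken by itself, the synopsis sentence leaves out futility and safety concerns, which the body lists. Its main clause, which speaks only of efficacy, also fits poorly with its own bracket, which includes harm.

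Second, the consistency check in 5.7 applies to any early stop. For benefit it is a sensible brake, because it guards against acting on a chance finding in one trial. For harm it points the wrong way. The outpatient trial counts hospital admission or death at an assumed risk of 12%; the inpatient trial counts ventilation or death at an assumed 30% in patients already in hospital. Harm confined to sicker patients need not appear as extra outpatient admissions.

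Death and ventilation are efficacy outcomes (4.5.1) and are not among the named safety outcomes (4.5.5). An excess of either would therefore be read first under the very sentences that carry the 3 SD guideline and the consistency check. At stake is how long inpatients continue to be randomised to a worse arm.

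**Working it through.** **1. Reproduce the plan's own figure.** Section 4.6.1 sets 265 per arm "in order to have 90% statistical power to detect a 40% relative risk reduction (RRR) in the proportion progressing to mechanical ventilation or death", with a usual-care risk of 30%. A 40% reduction gives 18%. Section 4.6.2 states: "All results will be analyzed with 2-sided level of significance of 0.05".

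n per arm = [1.960·√(2·p̄(1−p̄)) + 1.282·√(p₁(1−p₁) + p₂(1−p₂))]² / (p₁−p₂)², with p̄ = 0.24

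= [1.960·√0.3648 + 1.282·√0.3576]² / 0.12² ≈ 3.80 / 0.0144 ≈ 264.1, so 265 per arm and 530 in total. This matches.

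**2. What 3 SD means for harm.** Pooled Z = (p_T − p_C) / √(p̄(1−p̄)·2/n). At 100 per arm with 30% under usual care, 51% under AZCT gives p̄ = 0.405 and Z = 0.21 / 0.0694 = 3.02. At 50%, Z = 0.20 / 0.0693 = 2.89, which does not cross.

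**3. Chance of stopping for harm.** Method: binomial simulation of the inpatient trial, usual-care risk 30%, a look every 50 patients (10 looks before 530), and a stop when Z ≥ 3 towards harm. Loss is taken as zero, since "we assumed minimal (<1%) loss to follow-up". The protocol gives no harm effect, so the AZCT risk is varied as an assumption. Outcomes are treated as known at once.

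Two readings of consistency are shown. In both, the outpatient trial must have more events under AZCT at the same look, and it accrues in the ratio 1000 to 530. In the first its true risk ratio is 1. In the second it equals the inpatient risk ratio.

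| Inpatient risk, usual care vs AZCT | 3 SD alone: stop early | Mean N of 530 | With check, outpatient RR = 1 | With check, same RR |
|---|---|---|---|---|
| 30% vs 36% | 10% | 508 | 5.5% | 9% |
| 30% vs 40% | 33% | about 460 | 19% | 31% |
| 30% vs 42% | 50% | about 420 | 30% | 49% |
| 30% vs 45% | 74% | about 352 | 46% | 74% |
| 30% vs 50% | 96% | 242 | 64% | 96% |

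With the check and an outpatient RR of 1, mean N rises from about 460 to about 492 at 30% versus 40%, and from about 352 to about 427 at 30% versus 45%.

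**4. Sensitivity to delayed outcomes, without the consistency check.** If only complete 45-day outcomes count and inpatient accrual takes 6 months, about 530 × 45/180 ≈ 132 patients are in the pipeline at any look. Early stopping then falls to 20% (30% vs 40%) and 53% (30% vs 45%). With 3 months' accrual it falls to 12% and 34%. The 3 to 6 months is borrowed from the outpatient section (3.7.1), because no inpatient accrual time is given.

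**The case against.** The strongest reply is that none of this binds the DSMC. The 3 SD limit is a general guideline within a flexible approach, consistency is something the committee looks for and not a stated precondition, and each trial is considered separately. Safety concerns are an independent ground for stopping, with no SD threshold and no cross-trial condition. Section 5.1.1 has the DSMC review efficacy and safety outcomes on an ongoing basis. A trial trending to harm would also tend to meet the futility ground. A charter, not at hand, may settle the detail.

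Most of that stands, and it rules out three stronger readings.

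- A reader might infer that the synopsis forbids stopping for harm. Its bracket names harm, so it does not. The sentence is inconsistent with itself and incomplete against the body.
- A reader might infer that a harmful inpatient regimen would usually run close to full size. The table supports that only for moderate harm. At 30% versus 45% the boundary alone stops about three trials in four. The simulation also leaves out the separate safety and futility routes.
- A reader might infer that the harm boundary itself is an error and should be lowered, for example to 2.5 SD. At 30% versus 40% that would stop 54% of trials (mean N 393), but false harm stops under no effect would rise from about 0.7% to about 3%. That is a trade-off. The protocol states its symmetric choice openly, and nothing in it makes the choice wrong.

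Discretion does not, however, repair the two sentences. The synopsis still disagrees with 3.3.3 and 4.3.3, and the consistency sentence still covers every early stop. A charter should not have to override its protocol.

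**Conclusion.** The point holds in limited form. The synopsis and body conflict on the grounds for early stopping, and the consistency check is worded to apply to harm although the two trials need not agree on harm.

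The size depends on how the check is used. If agreement in direction were required and the true outpatient effect were nil, the chance of an early inpatient harm stop under the 3 SD guideline would fall from about 33% to 19% at 30% versus 40%, and from about 74% to 46% at 30% versus 45%. If the outpatient trial shared the same risk ratio, the check would change little. These figures rest on assumed harm effects, immediate outcomes, looks every 50 patients and one reading of consistency that the protocol does not define. They describe the boundary and the check only, not the whole of the DSMC's monitoring.

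**What to change.** 1. Reconcile the synopsis sentence on stopping with the grounds listed in 3.3.3 and 4.3.3, so that every section gives the same list and the main clause agrees with its bracket.
2. In the synopsis and 5.7, limit the cross-trial consistency check to stopping for benefit, and state that harm is judged in each trial separately.
3. Carry the same wording into the DSMC charter.

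The cost is a few lines of protocol and charter text. The 3 SD guideline, the sample size and the final significance level stay as they are. Exempting harm from the check cannot raise the chance of a false claim of benefit. The chance of a false inpatient harm stop stays at about 0.7%, the figure for the 3 SD boundary without the check.

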- Adaptive sample size: Sample size calculations are based on disease progression rates that are not well known. We remain flexible, and the DSMC will be monitoring the possibility that the assumptions for sample size calculations may be modified with emerging information from this trial or other ongoing trials. If necessary, sample size may be increased accordingly.

Analysis: The primary hypothesis of efficacy will be conducted under the intention-to-treat principle; all randomized participants will be included in the analyses. Each trial will be analyzed separately with 2-sided level of significance of 0.05. No modification of the level of significance is necessary with the 3 SD boundary for the Haybittle-Peto criteria.

Outpatient trial: The primary analysis will use the Z-test for comparison of proportions. Secondary analyses will include adjusting

	the intervention effect for demographic and exposure characteristics of the participants using logistic regression models.
	Inpatient trial: The primary analysis will use the Z-test for comparison of proportions. Secondary analyses will include adjusting the intervention effect for demographics, exposure characteristics, and severity of disease upon admission, using logistic regression models.
Duration of Study Period (per subject)	Patients will be followed for 45 days from randomization in both trials and will receive a telephone call at 1 year to evaluate vital status.

1. Program Background

A novel severe acute respiratory syndrome coronavirus 2 (SARS-CoV-2) has affected hundreds of thousands of people worldwide. The disease that is now known as COVID-19 was first reported to the World Health Organization on December 31, 2019. The disease is spreading quickly around the globe and has been declared a pandemic on March 11, 2020. Exploring therapies potentially of benefit for COVID-19 is a public health emergency.

Chloroquine and azithromycin in combination have shown promise in treating COVID-19. In vitro, chloroquine increases the endosomal pH required for the virus to fuse with cells, interferes with the glycosylation of SARS-CoV-2 cell receptors, thereby blocking viral infection. Investigators performed a time-of-addition assay which showed that chloroquine is effective at both the entry and post-entry stages of the SARS-CoV-2 infection in cells. Azithromycin is a macrolide antibiotic that has been found to inhibit the viral tropism and replication of Zika and Ebola viruses. 3-5

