Preventing people infected with COVID-19 from developing severe enough symptoms to require hospitalization is as important as treating people with COVID-19 pneumonia from deteriorating and needing ventilation or experiencing death. Therefore, we have established a program that includes two parallel trials; an **outpatient trial** seeking to prevent hospital admission and mortality, and an **inpatient trial** seeking to prevent need for mechanical ventilation or mortality. This program is a priority. If this therapy is proven conclusively to be effective, it will be used around the world. If it proves ineffective, other treatments will be explored emergently using the platform we (and other investigators) will establish.

As we design the trials, we acknowledge that many of the details usually available to design a study are not reliably available. This includes event rates (although we have made the best estimate using available data), potential size of the study or the numbers of cases that can be enrolled within a reasonable period as the number of cases is expected to increase rapidly in Canada and in many other countries). We have therefore designed these trials using the best available data, our judgement and with the goal of recruiting as many patients as possible (but at least 1000 into an outpatient trial and at least 530 into the inpatient trial). We have also built in two key mechanistic substudies testing the effects of the regimen on viral loads and on inflammation – to get an early indication of potential efficacy. During the conduct of the trials, we may need to make adjustments to several aspects of study design. To enable this and to monitor safety, the trial data will be reviewed periodically by an expert and independent data and safety monitoring committee (DSMC). We may also consider adding new arms or replacing existing arms (if they are shown to be ineffective based on emerging data) as promising new treatments emerge.

2. Program Hypothesis

Azithromycin in combination with chloroquine therapy (AZCT) on top of usual care will reduce disease progression of COVID-19 compared to usual care.

3. Outpatient trial: Preventing disease progression in COVID positive outpatients

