3.3.3 Adaptive design features

Adaptive intervention arms: The DSMC and the Steering Committee will keep abreast of other ongoing trials and, if a more promising intervention is emerging, may recommend adding (or replacing) one arm with the new promising intervention. They will also assess the results of the translational objectives when available and may add a chloroquine loading dose if a rapid or large reduction in viral titres is not observed with the current regimen.

Adaptive sample size: Sample size calculations are based on disease progression rates that are not well known. The DSMC will monitor the possibility that the assumptions for sample size calculations may be modified with emerging information from this trial or other ongoing trials. If recruitment is going well, the steering committee may decide to extend recruitment as long as the independent DSMC does not terminate the trial for clear evidence of efficacy, futility (or low likelihood) to detect a clinically meaningful difference (e.g. a 20% RRR in events) or concerns about safety.

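### Reviews about every 50 patients at 3 SD followed by an unadjusted 0.05 test give about 5.7% (inpatient) and 6.1% (outpatient) type I error, so the protocol's claim that the final level needs no change is not correct

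*Protocol*

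**What the plan says.** **Look schedule.** Section 5.7: "An independent DSMC will review the accumulating study data after approximately every 50 patients have been randomized". The synopsis, under adaptive termination, says the same and links these reviews to stopping for efficacy: "They will review accumulating data after every 50 subjects have been randomized". The DSMC may change the frequency.

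**Boundary.** Section 5.7: "They will follow a modified Haybittle-Peto boundary of 3 SD for benefit and harm as a general guideline". The DSMC also wants efficacy results to be consistent across the two trials before it recommends an early stop. That condition is not quantified.

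**Final level.** Synopsis, Analysis: "Each trial will be analyzed separately with 2-sided level of significance of 0.05", followed by "No modification of the level of significance is necessary with the 3 SD boundary for the Haybittle-Peto criteria". Section 5.7 repeats the claim: "No modification of the level of significance of the final results is necessary with the higher 3 SD boundary for the Haybittle-Peto criteria". Sections 3.7.2 and 4.6.2 also give two-sided 0.05.

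**Sample size.** The figures of 1000 and 530 are minimums (sections 3.2.2 and 4.2.2), and no maximum is given. Section 1 describes the design as made "with the goal of recruiting as many patients as possible". Section 3.3.3 adds: "If recruitment is going well, the steering committee may decide to extend recruitment", unless the DSMC terminates the trial; section 4.3.3 has the same rule. Both sections and the synopsis allow the sample-size assumptions to change with information from this trial, without saying whether that means pooled data or data by arm.

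**The concern.** A Haybittle-Peto rule can leave the final level alone because a few very strict interim looks spend almost no alpha. That depends on there being few looks. At 3 SD each look has a nominal two-sided p of 0.0027, and with 10 or 19 looks the total spent is no longer negligible. Adding a full 0.05 test at the end takes the overall error above the stated 0.05.

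The practical consequence falls on borderline results. At the minimum size with all looks taken, a final p between about 0.043 and 0.05 (inpatient) or between about 0.039 and 0.05 (outpatient) would be declared significant although the 5% error rate is not met. Section 1 expects a conclusively positive result to change practice worldwide, so the stated error rate should be the one delivered.

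**Working it through.** **1. The plan's own sample sizes, as a baseline.** Per-arm formula for two proportions, two-sided 0.05, 90% power, pooled variance under the null:

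n = [1.960·√(2p̄(1−p̄)) + 1.2816·√(p₁(1−p₁) + p₂(1−p₂))]² / (p₁−p₂)²

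- Outpatient (12% against 6%, p̄ = 0.09): (0.7932 + 0.5158)² / 0.0036 gives 477 per arm. With the 3% loss of section 3.7.1, 477/0.97 gives 492. The stated 500 is consistent with this.
- Inpatient (30% against 18%, p̄ = 0.24): (1.1838 + 0.7664)² / 0.0144 gives 265 per arm, exactly the figure in section 4.6.1.

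Both calculations use a fixed-sample 0.05 test, so no alpha has been set aside for interim looks.

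**2. Number of looks at the minimum size.** Outpatient: 1000/50 = 20, the last being the final analysis, so 19 interim looks. Inpatient: 530/50 = 10.6, so 10 interim looks.

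**3. Overall error under the null.** The test statistic is treated as a Brownian score process with information proportional to the number of patients. The trial stops if |Z| ≥ 3 at any interim look; otherwise it is tested at |Z| ≥ 1.96. Overall error = P(cross 3 at some interim look) + P(no crossing, then |Z| ≥ 1.96 at the end), found by recursive numerical integration.

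| Trial | Interim looks | Spent at interims | Added at final test | Overall |
|---|---|---|---|---|
| Inpatient, N = 530 | 10 | 0.0144 | 0.0424 | 0.0568 |
| Outpatient, N = 1000 | 19 | 0.0195 | 0.0411 | 0.0606 |

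Binomial simulation of the pooled Z-test agrees: about 0.058 (530, 30% risk) and 0.059 (1000, 12% risk).

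**4. When the claim is nearly true.** Equally spaced 3 SD looks with a final 1.96 give 0.0508, 0.0517 and 0.0525 for one, two and three looks.

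**5. Sensitivity to how the plan is run.**

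| Condition | Inpatient | Outpatient |
|---|---|---|
| Looks every 100 patients | 0.053 | 0.056 |
| Stop only if the other trial points the same way (assumed form of the consistency condition) | 0.054 | 0.056 |
| No boundary crossing ever acted on | 0.050 | 0.050 |
| Extended without regard to the result, single final test (530 to 795–1590; 1000 to 1500–3000) | 0.059–0.064 | 0.063–0.069 |
| 0.05 test at the minimum N, one extension of 50–200% if not significant | 0.083–0.096 | 0.087–0.099 |

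The last row is a hypothetical that the protocol does not describe.

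**6. Final critical value that restores 0.05 at the minimum N.**

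| Design | Final critical value | Nominal p | Power, unadjusted → adjusted |
|---|---|---|---|
| Inpatient, all 10 looks | 2.02 | 0.043 | 0.90 → 0.89 |
| Outpatient, all 19 looks | 2.07 | 0.039 | 0.91 → 0.89 |
| Three looks at 25/50/75% | 1.98 | 0.047 | loss of about 0.4 points |

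The power figures use the protocol's effect sizes, with 265 per arm (inpatient) and 485 per arm (outpatient, 500 less 3%). Before rounding, the loss with all looks kept is about 1.1 points (inpatient) and 1.8 points (outpatient).

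**The case against.** The strongest reply is that 5.7% and 6.1% are upper readings of the look schedule. The 3 SD boundary is a guideline, the DSMC may look less often, and it seeks agreement between the trials before stopping. Each of these lowers the error, as step 5 shows, and a separate charter, not available here, may set fewer efficacy looks. This stands as a limit on the size of the problem. It does not rescue the sentence, which is stated as fact beside a schedule of about one look per 50 patients. A charter that limited the looks would reduce the excess but would leave the claim uncorrected in the protocol.

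A reader might also infer that the open-ended sample size puts the error at 9 to 11%. The protocol does not support that. Such figures need a formal 0.05 test at the minimum size and an extension because it failed. No such test is planned, and sections 3.3.3 and 4.3.3 tie extension to recruitment. Even on that assumption, one extension of 50 to 200% gives about 8 to 10%; more than that needs two failed tests or a five- to tenfold extension.

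Nor do the documents say that results by arm will drive changes in sample size. The stated reason is that progression rates are poorly known, which suggests updating an event rate. The weakness is that the text does not rule the other course out.

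**Conclusion.** The statement that the final level needs no modification is wrong for the schedule the protocol sets. At the minimum sample sizes, with every look acted on at 3 SD and full outcome data at each look, the overall two-sided error is about 5.7% (inpatient) and 6.1% (outpatient), an excess of 0.7 and 1.1 points over the stated 0.05. The excess shrinks if looks are fewer or the consistency condition is applied. It grows to about 6 to 7% overall if recruitment is extended independently of the result. The range of about 8 to 10% belongs only to an extension that follows a non-significant 0.05 test, which the protocol neither plans nor excludes. The defect is modest and cheap to repair: it should be fixed, but it does not undermine the design.

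**What to change.** 1. Delete the sentence in section 5.7 and its counterpart in the synopsis.
2. Keep the reviews every 50 patients for safety. For efficacy, choose one of two routes:
   - a few formal looks, for example three, with a final critical value of about 1.98; or
   - an alpha-spending function with the matching final level. If all looks are kept at the minimum N, this is about |Z| ≥ 2.02 (p < 0.043) for the inpatient trial and |Z| ≥ 2.07 (p < 0.039) for the outpatient trial. A spending function suits a look frequency that the DSMC may change.
3. State that any increase in sample size is decided from pooled event rates, external data or recruitment, by people blind to results by arm, and that the final critical value is recomputed for the looks actually taken.

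The cost is wording in the protocol and the DSMC charter, plus a slightly stricter final test: about 0.4 points of power with three looks, and about 1 to 2 points with all looks kept. The critical values come from normal theory and should be checked against the binomial test when the looks are fixed.
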